## 3. Purpose

Drug overdose is the leading cause of accidental death in the United States (US) and prescription pain reliever addiction is driving this epidemic (Center for Disease Control and Prevention [CDC], 2015). There are enough opioid prescriptions written each year to provide every single adult American one bottle of pills (e.g., 259 million prescriptions in 2012) (CDC, 2014) and 78 Americans die every day from an opioid overdose (CDC, 2016). Pain is the most universal medical complaint with 25% of US adults reporting a day-long episode of pain over the previous month and 10% reporting the pain lasted a year or more (National Center for Health Statistics, 2006). Pain and its sequela (including those directly linked to opioid use/abuse) cost the US economy 61.2 billion per year (Stewart, Ricci, Chee, Morganstein, & Lipton, 2003). Accordingly, finding new methods of reducing pain is a priority for the US government. Indeed, on March 18, 2016 the CDC released new guidelines for reducing opioid prescriptions (Dowell, Haegerich, & Chou, 2016) and on March 29, 2016 the White House released a document detailing the actions needed to address this public health problem (The White House, 2016). Both of these documents call for non-medication methods of pain management.

Virtual Reality (VR) is one effective non-pharmacological method that reduces acute and chronic pain. A systematic review of 11 randomized controlled trials (i.e., gold standard for evaluating intervention efficacy) showed that VR reduced pain more than credible control interventions (Malloy & Milling, 2010). Importantly, pointing to room for improvement to current VR interventions for pain, this analysis showed that the level of pain reduction was dependent on how realistic the virtual environments were. There are two primary problems with current VR technology that prevent large-scale use and effectiveness. First, current VR technology uses animated (cartoon like) environments (see Figure 1). Patients report this quality prevents full immersion. Studies have shown that many users complain that the computer generated virtual reality (VR) stimuli looks unrealistic, eccentric and too much like a video game (Kwon, Powell, & Chalmers, 2013). Virtual reality environments have been traditionally created by programmers using video game assets and computer generated imagery (CGI). While CGI can be used to make intricate virtual environments, unless there is a team of

The University of Texas at Austin

Institutional Review Board- Revised October 2014

Figure 1. Example of current VR

Figure 2. Example of current VR  
Virtual reality environments have been traditionally created by programmers using video game assets and computer generated imagery (CGI). While CGI can be used to make intricate virtual environments, unless there is a team of

## Research Proposal

---

expert digital artists, the virtual stimulus may end up looking rudimentary and exhibit a number of graphical glitches, which could prove distracting in therapy. Furthermore CGI often suffers from the uncanny valley effect: the tendency of CGI representations of people to be viewed as unsettling as the representations become more lifelike. Second, current CGI VR technology is bulky and costly requiring a large computer setup with multiple screens (approximately \$30,000 for a setup; see Figure 2). Recent advances in VR technology can address both of these concerns, and thus there is potential to develop a more cost-effective application.

Our team has been working with virtual reality for 10 years now conducting several large randomized controlled trials (Powers & Emmelkamp, 2008; Meyerbröker, Powers, van Stegeren, & Emmelkamp, 2012; Powers et al., 2013; Tart et al., 2013). Two major recent innovations are central to this proposal. First, the realism possible in VR has dramatically increased with the use of 360-degree 3D HD film environments. 360-Degree Video VR is a radical filmmaking technology that can turn live action footage into a 360-degree environment that users can interact with. 360-Degree Video VR is made by filming with an array of multiple HD cameras carefully arranged to capture all angles in a 360-degree area of a live action event (see Figure 3). Then those angles are stitched together in post-production into a 360-degree texture sphere and the sphere is then mapped to the head tracker on the users HDM. Leading to the effect that when a user turns his head, their view of the live action video footage turns with them in real time (e.g. if the user looks down, the camera pans down and the user sees the floor) allowing the user to look around anywhere in the 360 degrees of filmed footage of the live action event. The benefit of 360-Degree Video VR as opposed to CGI VR is that it is photo realistic, does not suffer from the uncanny valley effect of CGI, and is able to capture nuances of real life fears that are hard to reproduce with CGI. In addition, the projected cost of the end product is approximately \$500. This enhanced level of immersion has the potential to dramatically improve the efficacy to reduce acute and chronic pain (see above). Second, deployment of the resulting content to patients is now much smaller and inexpensive (e.g., \$99 for a Samsung Galaxy Gear VR (see Figure 4) or \$20 for Google Cardboard systems). This technology makes VR accessible to anyone with a smartphone.

The current study seeks to test the efficacy of the standard animated/CGI VR versus the enhanced 360-degree 3D HD film versions of VR in reducing pain in hospital patients. To this aim we will enroll 201 adult participants experiencing pain University Medical Center Brackenridge (UMCB), Dell Seton Medical Center (DSMC), Baylor Scott & White Medical Center Temple (BSWMCT), and randomly assign them to the enhanced (360-Degree Video VR) film condition ( $n = 67$ ), the standard (animated/CGI film) condition ( $n = 67$ ), or the waitlist

Figure 3. 360-degree

Figure 4. New affordable delivery

## Research Proposal

---

condition ( $n = 67$ ). We anticipate we will need to recruit and consent a total of 500 participants due to the anticipated number of screen failures (due to inclusion/exclusion criteria). We hypothesize that the film VR will show greater pain reductions and increased functioning relative to both the animated VR and the waitlist condition.

### 4. Procedures

#### **Hospital Study Visit**

Data collection will be completed in a single visit to the participant at University Medical Center Brackenridge Hospital, Dell Seton Medical Center, or **Baylor Scott & White Medical Center Temple** and an online follow-up questionnaire e-mailed to the participant approximately one-week after study visit completion. If email is not available for the follow-up survey, participants will be reached by telephone. Total participation in the hospital visit will be approximately 1 hour. The follow-up survey will take participants 10-15 minutes to complete. Prior to gathering data, research personnel will receive proper training in order to interact with the hospital patients and will follow all hospital procedures during the study visit.

#### Recruitment

Our Seton PI, [name], will connect research personnel with hospital staff at UMCB and (DSMC) who care for patients experiencing pain. Hospital staff will refer patients to research personnel that meet eligibility criteria for the study and may be a potentially eligible participant. Patient information necessary to conduct an in-person recruitment visit by study personnel (patient name and hospital room number) will be shared by hospital staff with research personnel through the standard secure email (Ascension Secure E-mail Portal) or texting (TigerText) applications used by UMCB and (DSMC). Both of these applications are regularly used by UMCB and (DSMC) staff to share Protected Health Information (PHI) with hospital staff. Ascension Secure E-mail Portal and TigerText keep messages confidential and are HIPAA compliant. Additionally, potential participant information may be shared with research personnel during in-person morning hospital rounds. Hospital staff may supply potential participants with information regarding the study found in the Recruitment Announcement, but will not be involved with direct recruitment. All direct recruitment will be conducted by research personnel. This method of recruitment is the standard used by UMCB and (DSMC) and is the preferred manner of recruitment by hospital staff.

Our BSWMCT PI, [name], will connect research personnel with hospital staff at BSWMCT who care for patients experiencing pain. Hospital staff will refer patients to research personnel that meet eligibility criteria for the study and may be a potentially eligible participant. Patient information necessary to conduct an in-person recruitment visit by study personnel (patient name and hospital room number) will be shared by hospital staff with research personnel in-person, over the phone, or in email over the secure hospital network. All direct recruitment will be conducted by research personnel.

## Research Proposal

---

Research personnel will meet with the potential participant in their hospital room to recruit the patient for the study. If the patient is interested in participating, the research personnel will conduct the in-person study visit at that time, or return at a time specified by the patient. At the start of the study visit research personnel will go over the consent form with eligible participants and answer any questions they may have about the study procedures. Participants will be able to continue on with the study if they are able and willing to give signed informed consent. Following consent, participants will be asked, if they are willing, to complete and sign the HIPAA Research Authorization form to permit research personnel to access their medical records. Information collected from the medical records will include self-report pain ratings, medication information (names, doses, and timing), hospital room number, phone number, email address, date of birth, medical diagnosis information, and medical progress notes. If participants refuse to sign the HIPAA Research Authorization, they will still be allowed to participate in the study, but their medical records will not be accessed by research personnel.

During a 15-minute baseline, participants will be assessed for consciousness by study personnel (Glasgow Coma Scale & abbreviated Mini Mental Status Exam) and then complete a short battery of questionnaires to obtain demographic, treatment, and prior media use information, and to assess their mood, average pain, and pain interference levels. All assessments will be delivered on an electronic iPad or on paper. All assessments are designed to be able to be delivered orally if participants cannot use the iPad or utilize a pen or pencil.

### Conditions

Participants will be randomized to the 360° 3D HD video VR film condition, animated video VR condition, or waitlist condition. Those randomized to the waitlist group will complete all study procedures except the VR exposure. After completion of the study visit, we will give those in the waitlist condition the option of experiencing the 9-minute VR video of their choosing.

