### Post-Treatment Assessments

Following the 9 minutes of VR exposure or waiting, participants in each condition will complete post-treatment assessments for 5-10 minutes. These assessments will measure pain, presence, mood, negative effects of VR, absorption, human presence, participant's prior familiarity with the locations depicted in the VR video, and their attitude toward the VR session immediately after the treatment. Nausea, dizziness, eyestrain, and head pain is being assessed in an effort to identify the incidence of this component of simulator sickness sometimes associated with VR use (Kennedy et al., 1992). Following the Post-Treatment assessments, the Follow-Up Pain Questionnaire & Present Mood Questionnaire will be administered 10 minutes following the treatment. These follow-up assessments are in place in order to track the lasting pain reduction from the VR treatments.

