### One-week E-mail Follow-up

One-week after participating in the experiment participants will be e-mailed a series of follow-up questionnaires that will include the Follow-Up Pain Questionnaire, Present Mood Questionnaire, and Participant Satisfaction Survey. If participants cannot be reached by email, research personnel will contact them via telephone or a follow-up in person interview.

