## Hospital Study Visit Overview

1. Obtain Informed Consent
2. Baseline Assessment (15 minutes)
  - a. Assess consciousness
    - i. Glasgow Coma Scale
    - ii. Mini Mental Status Exam
  - b. Demographic Questionnaire
  - c. Media Use Survey
  - d. Personal Health Questionnaire-8
  - e. Pre-Treatment Pain Questionnaire
  - f. Present Mood Questionnaire
3. Treatment Conditions
  - a. Film VR condition (30 minutes)
    - i. Samsung Gear VR information session
      1. Participants will receive information describing the Gear VR and instructed to fully engage with the VR video.
    - ii. Samsung Gear VR Fitting
      1. Gear VR will be adjusted to participant's head
    - iii. Watch 9 minute 360° 3D HD VVR film
    - iv. Administer Post-Treatment Assessments (5-10 minutes)
      1. Post-Treatment Pain Questionnaire
      2. Present Mood Questionnaire
      3. Presence Inventory
      4. Absorption Survey
      5. Attitudes Toward the Experience Survey
      6. Human Presence Survey
      7. Location Familiarity Survey
    - v. Wait 10 minutes
    - vi. Administer both the Follow-Up Pain Questionnaire & Present Mood Questionnaire (3-5 minutes)

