## Research Proposal

---

- b. Animated VR condition (30 minutes)
    - i. Samsung Gear VR information session
      1. Participants will receive information describing the Gear VR and instructed to fully engage with the VR video.
    - ii. Samsung Gear VR Fitting
      1. Gear VR will be adjusted to participant's head
    - iii. Watch 9-minute animated film
    - iv. Administer Post-Treatment Assessments (5-10 minutes)
      1. Post-Treatment Pain Questionnaire
      2. Present Mood Questionnaire
      3. Presence Inventory
      4. Absorption Survey
      5. Attitudes Toward the Experience Survey
      6. Human Presence Survey
      7. Location Familiarity Survey
    - v. Wait 10 minutes
    - vi. Administer both the Follow-Up Pain Questionnaire and Present Mood Questionnaire (3-5 minutes)
  - c. Waitlist condition
    - i. Participants will be directed to wait patiently for 9 minutes
    - ii. Administer both the Follow-Up Pain Questionnaire & Present Mood Questionnaire (3-5 minutes)
    - iii. Participants can choose to watch one of the two treatment VR videos for 9 minutes.
      1. Administer Post-Treatment Pain Questionnaire
4. Open Interview (3-5 minutes)
  5. One-week e-mail follow-up (10-15 minutes)
    - a. Follow-Up Pain Questionnaire
    - b. Present Mood Questionnaire
    - c. Participant Satisfaction Survey

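### The in-visit assessment meant to show lasting pain relief has no VR-free waitlist match at the same time, and the one-week forms cannot supply one

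*Protocol*

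**What the plan says.** Section 3 (Purpose) hypothesises that film VR will show "greater pain reductions and increased functioning relative to both the animated VR and the waitlist condition". It names no time point.

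On what the waitlist completes, Section 4 gives two accounts.

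- **Narrative.** Under Conditions: "Those randomized to the waitlist group will complete all study procedures except the VR exposure". Under Post-Treatment Assessments: "participants in each condition will complete post-treatment assessments for 5-10 minutes", followed by the Follow-Up Pain and Present Mood questionnaires 10 minutes after treatment. Of these last forms the protocol says: "These follow-up assessments are in place in order to track the lasting pain reduction from the VR treatments".
- **Hospital Study Visit Overview.** The VR arms complete the post-treatment battery (5-10 minutes), wait 10 minutes, then complete the Follow-Up Pain and Present Mood questionnaires. The waitlist waits 9 minutes and goes straight to the Follow-Up Pain and Present Mood questionnaires (step 3.c.ii). Then comes the offer (step 3.c.iii): "Participants can choose to watch one of the two treatment VR videos for 9 minutes". The waitlist's Post-Treatment Pain Questionnaire follows that video (step 3.c.iii.1).

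Conditions places the offer after the study visit ("we will give those in the waitlist condition the option of experiencing the 9-minute VR video of their choosing"), and the Overview places it within the visit. Both put it before the one-week forms: "One-week after participating in the experiment participants will be e-mailed a series of follow-up questionnaires that will include the Follow-Up Pain Questionnaire". No arm is excepted from those forms.

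Section 5 (Measures) says the Post-Treatment form asks about pain during the VR session. The Follow-Up form is identical except that it asks about the last 10 minutes.

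**The concern.** The waitlist is the only arm that can show what pain does over the same interval without VR. To claim that relief persists after the headset comes off, one needs waitlist ratings at the same delay from patients who have not had VR. If staff follow the Overview, those ratings are never collected. An analyst would be left with three substitutes:

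- the waitlist's rating straight after the wait, set against a later rating in the VR arms;
- the waitlist's Post-Treatment form, which is completed only after VR;
- the one-week forms, by which time some of the waitlist may have watched either video.

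None of these compares VR with no VR at the time the protocol ties to lasting relief. Ratings not taken at the visit cannot be recovered by a later analysis plan.

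**Working it through.** **In-visit schedule under the Overview.** Time zero is the end of the 9-minute video or wait.

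| Assessment | VR arms | Waitlist |
|---|---|---|
| Straight after | Post-Treatment form, about the VR session | Follow-Up form, about the last 10 minutes |
| Follow-up in the visit | Follow-Up form at 5 + 10 = 15 to 10 + 10 = 20 minutes (Post-Treatment Assessments says 10 minutes after treatment) | None before the offer |
| After the optional video | Not applicable | Post-Treatment form, takers only |

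**Straight after.** The items are the same, since the forms differ only in recall window. A 10-minute window given straight after a 9-minute wait covers that wait plus about one minute. This comparison is nearly matched and precedes the offer. The mood questionnaire is also given to every arm at this stage.

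**Follow-up.** The waitlist's Follow-Up form covers about the 10 minutes *before* time zero. The VR arms' form covers 0 to 10 minutes *after* it (narrative timing), or 5 to 15 up to 10 to 20 minutes after it (Overview timing). The windows do not overlap on either timing. Pairing by form name therefore fails in both directions: Follow-Up against Follow-Up compares different periods, and Post-Treatment against Post-Treatment compares VR with VR.

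**One week.** The target is 3 x 67 = 201 participants. The text shown gives neither waitlist uptake of VR nor a one-week effect, so the following is illustration under assumptions. Let *d* be the film-versus-no-VR effect at one week in SD units, *u* the uptake, and *r* the share of that effect that takers gain:

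remaining difference = *d* x (1 - *u* x *r*)

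At *u* = 50% this leaves 100%, 75% or 50% of the effect for *r* = 0, 0.5 or 1. At *u* = 75% it leaves 100%, 62.5% or 25%.

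Power of a two-sample t-test with 67 per arm and two-sided alpha 0.05 (assumed):

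| *d* | No dilution | *u* = 50%, *r* = 0.5 | *u* = 50%, *r* = 1 |
|---|---|---|---|
| 0 | 5% | 5% | 5% |
| 0.1 | 9% | 7% | 6% |
| 0.2 | 21% | 14% | 9% |
| 0.3 | 41% | 25% | 14% |
| 0.5 | 82% | 58% | 30% |

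The 95% confidence interval half-width is 1.978 x sqrt(2/67) = 0.34 SD. Dilution matters little if the one-week effect is near zero and a good deal if it is moderate. *r* = 1 is an upper extreme, because takers may choose the animated video, which the protocol expects to work less well than film.

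**The case against.** The strongest reply is that a waitlist arm is openly a deferred-treatment arm. The protocol declares the later offer, and nowhere says that film will be tested against waitlist at one week or that one week is primary. It ties lasting relief to the 10-minute assessment. Which time points are tested and how contrasts are labelled can be left to a statistical analysis plan. The one-week pain form asks only about the last 10 minutes, and nothing in the protocol supports a moderate effect a week after 9 minutes of viewing.

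This largely stands. A reader might infer that the optional video contaminates the trial's main waitlist comparison, or that the one-week result is materially biased. The protocol supports neither. Waitlist ratings made before the offer are untouched, as is film versus animated VR at one week. A one-week waitlist contrast would still be randomised, and a positive difference could be read as immediate VR versus a delayed offer. The power loss rests wholly on assumed values.

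A second reply is that the Overview is only an outline and the narrative governs. That is possible, but the Overview is the only step-by-step schedule for the waitlist, and it sets out a different order and different forms. The text does not say which account prevails.

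It is also fair that the form at step 3.c.iii.1 identifies takers indirectly. It does not show which video was chosen, and no section says the choice is recorded.

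**Conclusion.** The point holds for the in-visit schedule. Followed as written, the Overview leaves the assessment that is meant to track lasting pain reduction without a VR-free waitlist rating at the same time. The gap is 10 minutes by the narrative and 15-20 minutes by the Overview, and the recall windows do not overlap. This contradicts Conditions and Post-Treatment Assessments. It needs no assumption beyond staff following the Overview. The immediate comparison is nearly matched and is not in dispute.

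The one-week forms do not repair the gap. A null one-week film-versus-waitlist result could not be read as no lasting effect of VR, because part of the control arm may have had VR. How much this matters depends on uptake and on any effect at one week, neither of which the protocol gives. The dilution is nil if there is no such effect. The schedule should be corrected, but the point does not undermine the trial's immediate comparisons.

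**What to change.** 1. Reconcile Conditions, Post-Treatment Assessments and the Hospital Study Visit Overview. All three arms should complete the same pain items straight after the 9-minute period and again at the in-visit follow-up, at one stated delay, before VR is offered to the waitlist. The item wording should make sense for a patient who only waited. State once when the offer is made.
2. State that VR-versus-no-VR inference uses these pre-offer assessments, and not the waitlist's Post-Treatment form at step 3.c.iii.1.
3. Describe any one-week waitlist contrast as immediate VR versus a delayed, optional offer of VR, analysed as randomised. Takers should not be dropped or reclassified, because uptake is self-selected. Film versus animated VR is the one-week comparison that the offer does not affect.
4. Record on the eCRF whether each waitlist patient took VR and which video.

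The offer itself stays. The cost is protocol wording, an eCRF entry, and about 10-20 more minutes for waitlist patients before the offer. The trial would make no one-week claim of VR against no VR.
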